4.2 Inclusion Criteria

The inclusion criteria comprise criterions which are applicable for all subjects (pre- and post-menopausal) as well as additional criterions exclusive to each sub-population. Only subjects to whom all the following conditions apply will be included.

4.2.1 Universal Inclusion Criteria

1. Subject and their male partner have provided written informed consent.
2. Subject is female and both subject and their male partner are aged at least 18 years. Maximum age of female subject is 65 years.

3. Subject and their male partner in a mutually monogamous heterosexual relationship (≥ 3 months) who are sexually active, defined as having sexual intercourse at least once a week. (Note: The number of sexual intercourses may comprise twice in one week to account for a menstrual period break.)
4. Female subject that agrees to have a gynaecological pelvic examination to ensure no significant disease findings and have intact skin and mucous in the test region (vaginal and vulvar / intimate area) except skin dryness as visually assessed by the gynaecologist at all the relevant time points.
5. Female subject that agrees to an oral exam by a dermatologist to ensure no significant disease findings and have intact skin and mucous in the test region (oral cavity - including lips, inside lining of the lips, cheeks (buccal mucosa), teeth, gums, tongue, the floor of the mouth, roof of the mouth (hard palate) and area behind wisdom teeth (retromolar trigone)).
6. Subjects reporting mild to moderate vaginal dryness and dyspareunia during sex (when not using lubricant) in the past 3 months as confirmed by a score of 1 or 2 for vaginal dryness and 1 or 2 for dyspareunia on the Verbal Rating Scale (VRS) of dyspareunia and vaginal dryness.

4.2.2 Pre-menopausal Inclusion Criteria

1. Female of childbearing potential who is willing to use a highly effective method of contraception throughout the clinical investigation. A female is considered to be of childbearing potential following menarche and until becoming post-menopausal unless permanently sterile by methods including hysterectomy, bilateral salpingectomy and bilateral oophorectomy. A highly effective method of contraception is defined as a method that can achieve a failure rate of less than 1% per year when used consistently and correctly. Such methods include combined (oestrogen and progestogen containing) hormonal contraception associated with inhibition of ovulation (oral, intravaginal and transdermal), progestogen-only hormonal contraception associated with inhibition of ovulation (oral, injectable and implantable), intrauterine device (IUD), intrauterine hormone-releasing system (IUS), bilateral tubal occlusion, vasectomised partner (who has received medical assessment of the surgical success) (Recommendations related to contraception and pregnancy testing in clinical trials, Clinical Trials Facilitation and Coordination Group, Version 1.1, 2020).

4.2.3 Post-menopausal Inclusion Criteria

1. Female subject in post-menopausal phase defined as having amenorrhea (absence of menstruation) for at least 12 consecutive months without an alternative medical cause (Recommendations related to contraception and pregnancy testing in clinical trials, Clinical Trials Facilitation and Coordination Group, Version 1.1, 2020).
2. Female subject with premature menopause – due to surgical menopause or physiological menopause within the last 12 consecutive months of the screening visit (diagnosis to be confirmed as irreversible in subjects' medical history) or after having received chemotherapy.

4.3 Exclusion Criteria

The exclusion criteria comprise criterions which are applicable for all subjects (pre- and post-menopausal) as well as additional criterions exclusive to each sub-population. Subjects to whom any of the following conditions apply must be excluded.

4.3.1 Universal Exclusion Criteria

1. Female subject or their partner who has previously experienced an irritant or allergic reaction to any personal lubricant, vaginal moisturiser or female hygiene product or known to have any contact allergy or allergy/ hypersensitivity to the test product ingredients.
2. Female subject with history of mucosal intolerance to warming agents.
3. Female subject with continuous or intermittent oral allergy syndrome or burning mouth syndrome, or history of thereof (self-reported).
4. Female subject with urinary, vaginal infection (fungal, bacterial) or sexually transmitted infection at screening visit, which in the opinion of the investigator would affect the study outcomes or the safety of the subject.
5. Female subject that has any condition of the oral cavity, including oral infection, active oral herpes simplex virus, active canker sores or oral ulcers and erosions as determined by the investigator.
6. Female subject who has had a positive cervical screening examination for human papillomavirus (HPV) within the 3 years of the screening visit (medical history/self-reported).
7. Female subject presenting with signs of internal irritation, active psoriasis, lichen sclerosis, eczema or other active skin disorder upon clinical examination.
8. Male partner of female subjects has broken skin or wounds in the intimate area (self-reported).
9. Female subject with a history of skin disorder, which in the opinion of the investigator will affect study outcome.
10. Female subject presenting clinically abnormal findings other than irritation e.g. lumps, open sores or blister type wounds during the physical examination (including the gynaecological examination) that in the opinion of the investigator will affect study outcome.
11. Female subject that has had a suspicion of malignancy or history of malignancy within the past 2 years (self-reported).
12. Female subject with autoimmune conditions or any medical conditions which in the opinion of the investigator could compromise the immune function.
13. Female subject who has had surgical cervical excision or vaginal and/or vulvar procedures, including laser and cosmetic procedures to the vulva or vagina in the previous year.
14. Female subject that has any tooth ache or other dental/oral malady (self- reported).
15. Female subject with ongoing dental/orthodontic procedures or any medical/surgical interventions involving the oral cavity (self-reported).

16. Female subject currently being treated with systemic medications or medicines (e.g. glucocorticosteroids, antibiotics, local oestrogen and other intravaginal products) that are acting locally in the vaginal area which may influence the clinical study outcomes.
17. Female subject who has started, stopped, or changed hormonal treatments (for contraception, vaginal dryness, or any other condition) during the previous 3 months prior to screening or those intending or expecting a change in treatment during the investigation.
18. Female subject who has used any kind of topical histamine and/or topical hormonal based product in the form of an intravaginal cream or moisturiser for local treatment of vaginal dryness in the past 3 months.
19. Female subject taking steroid preparations, immunosuppressants or any other medication which in the opinion of the investigator may affect the test results:
 - a. Anti-inflammatory or antihistamine within 1 week prior to the screening visit
 - b. Cough suppressants or corticosteroids within 4 weeks prior to screening visit.
 - c. Retinoids or immune suppressants within 6 months prior to screening visits.
20. Female subject who has had any change to medication or treatment regimen for the treatment of diabetes mellitus during the previous 3 months prior to screening.
21. Female subject using non-medicated, over the counter product, herbal/natural remedies on the vulva, vaginal opening and inside the vagina and is unwilling to stop at least 7 days prior to screening and throughout the duration of clinical investigation.
22. Female subject showing vaginal prolapse and/or other medical conditions that could interfere with the investigation conduct and participation.
23. Female subject using vaginal douches and is unwilling to stop its use at least 2 weeks prior to screening and throughout the duration of the clinical investigation.
24. Female subject or their male partner that, in the opinion of the investigator, will be unable to comply fully with the study requirements or unable to tolerate the procedures described in the CIP.
25. Female subject has participated in another investigation where a medicinal, medical device clinical investigation or any form of studies involved testing on female intimate area within 3 months prior to screening.
26. Female subject or their male partner has received an investigational product or participated in another trial involving a marketed or investigational drug in the 30 days (or for investigational agents with a long half-life, a washout of 5 half-lives) prior to screening. Or if the investigator believes that any previous participation in an investigational study would be to the detriment of the safety of the participant or the conduct of the study.
27. Female subject or their male partner who is an employee at the site or a partner or first-degree relative of the Investigator.
28. Female subject or their male partner fails to satisfy the investigator of fitness to participate for any other reason.

4.3.2 Pre-menopausal Exclusion Criteria

1. Female subject who is pregnant (as confirmed by a positive pregnancy test), breast-feeding or trying to conceive.

4.3.3 Post-menopausal Exclusion Criteria

1. Female subject that has had previous episodes of vaginal bleeding of unknown origin within the last 6 months of the screening visit.

4.3.4 Tolerance Subset - Exclusion Criteria for Enrolling into Treatment Phase

Subjects participating in the Tolerance Phase who have any of the following conditions must not continue to the Treatment Phase.

1. Any observed severe irritancy reactions at any time point.
2. Any reaction failing to adequately resolve or needing further treatment, that in the opinion of the investigator represents an unacceptable risk to proceed with the investigation.
3. Any AEs considered related to the investigational product that are serious and/or severe in nature that in the opinion of the investigator represent an unacceptable risk to proceed with the investigation.

4.4 Investigation Restrictions

4.4.1 Dietary and Lifestyle Restrictions

Dietary and Lifestyle restrictions for subjects and male partners are listed in Table 4-1 below:

Table 4-1 Dietary and Lifestyle Restrictions

Restriction	From	To	Applicable to female subjects	Applicable to male partners
Tolerance Phase and Treatment Phase				
Subjects are not permitted to use personal lubricant compounds other than the investigational product.	Screening	End of investigation	Yes	Yes
Subjects are not permitted to apply any products for the relief of vaginal dryness, other than the investigational product.	Screening	End of investigation	Yes	No

Restriction	From	To	Applicable to female subjects	Applicable to male partners
Subjects are not permitted to use their usual personal lubricants or remedies for vaginal dryness.	Screening	End of investigation	Yes	No
Subjects are not permitted to use any topical products on the intimate area.	Screening	End of investigation	Yes	Yes
Subjects should not change any topical skin product(s). (For use of topical products in the intimate area – see other restrictions.)	Screening	End of investigation	Yes	Yes
If bathing, subjects must not remain too long (longer than 10-15 minutes) in the water and not to use bath additives such as bath salts, bath oils etc.	Screening	End of investigation	Yes	Yes
Subjects are not permitted to change from their usual brand of sanitary products.	Screening	End of investigation	Yes	Yes
Subjects are not permitted to change the fabric detergent or fabric softener for clothes.	Screening	End of investigation	Yes	Yes
Subjects are not permitted to swim or bathe in chlorinated pool/spa or use jacuzzi tubs.	Screening	End of investigation	Yes	Yes
Subjects are not permitted to use washing implements such as wash cloths to wash the intimate area – only use hands.	Screening	End of investigation	Yes	Yes
Tolerance Phase				
Pre-menopausal women are not permitted to use tampons.	Screening	End of Tolerance Phase	Yes	No

Restriction	From	To	Applicable to female subjects	Applicable to male partners
Subjects are not permitted to use hygiene products or personal intimate grooming products in the intimate area (e.g. use of intimate washes, waxes, razor blade etc.) only water to be used in the intimate area.	Screening	End of Tolerance Phase	Yes	No
Subjects are to refrain from engaging in vaginal sex or any other vaginal penetrative sexual activity e.g. digital stimulation or use of sex toys.	Screening	End of Tolerance Phase	Yes	No
Subjects are not permitted to use any new oral products that are irregular to their normal dental hygiene routine or eating any new foods outside their normal diet.	Screening	End of Tolerance Phase	Yes	No
Treatment Phase				
No change in use of personal intimate hygiene products or personal intimate grooming products e.g. intimate washes, waxes, razor blade etc.	Screening (or End of Tolerance Phase for the tolerance subset)	End of investigation	Yes	Yes

4.4.2 General Restrictions

General investigation restrictions for subjects and male partners are listed in Table 4-2 below:

Table 4-2 General Restrictions

Restriction	From	To	Applicable to female subjects	Applicable to male partners

Avoid unprotected sexual intercourse for female subjects of childbearing potential.	28 days prior to Screening	End of investigation	Yes	No
Enrolment into another clinical investigation/study once participating in this investigation.	Screening	End of investigation	Yes	Yes
A change of partner.	Screening	End of investigation	Yes	Yes

4.5 Discontinuation / Withdrawal and Replacement of Subjects

The Investigator may withdraw the subject from the investigation at any time. Reasons for removing a subject from the investigation include, but are not limited to:

- AEs that in the judgement of the Investigator may cause severe or permanent harm (significant clinical deterioration is an AE)
- Violation of the CIP, which in the judgement of the Investigator affects subject's/male partner's safety or data integrity
- In the Investigator's judgement, it is in the subject's/male partner's best interest (this includes inadequate device performance)
- Subject/Male partner declines further investigation participation

The primary reason for withdrawal will be documented in the electronic case report form (eCRF).

For subjects who are lost to follow-up, at least 2 documented attempts should be made to contact the subjects for follow-up assessments which will include assessments as described for Visit 3 of the Tolerance Phase ([Section 7.3.3](#)) or Visit 3 of the Treatment Phase ([Section 7.4.3](#)).

30 subjects per treatment group are required to complete the 4-week Treatment Phase. A subset of 20 subjects is required to complete the Tolerance Phase. Subjects who withdraw from the investigation before receiving any IP will be replaced.

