6.12 Treatment Phase Variables

6.12.1 Female Sexual Function Index (FSFI)

The FSFI is a 19-item self-report questionnaire (paper) to measure sexual functioning in women. The questionnaire assesses six domains of sexual function (sexual desire, sexual arousal, lubrication, orgasm, satisfaction and pain) as well as a total score. The questionnaire requires a 4-week recall.

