6.12.4 Global Evaluation of Product Effectiveness, Tolerability and Usability

At the end of the Treatment Phase (or withdrawal if earlier) subjects will be asked to provide their global evaluation of their allocated IP after using their allocated IP for 4-week. Subjects will be asked to rate their agreement using the following scale:

- Very Satisfied
- Somewhat Satisfied
- Neither Satisfied nor Dissatisfied

- Somewhat Dissatisfied
- Very Dissatisfied

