6.12.5 Patients Global Impression of Change (PGIC)

At the end of the Treatment Phase (or withdrawal if earlier) subjects and male partners will be asked to complete a PGIC (Hugh H and Jennifer B, 2004). PGIC is a patient reported scale to assess patient perception of change in a condition or symptom following treatment. The subjects and male partners will be asked to rate the change in sexual intimacy experienced within their couple after using their allocated IP for 4-week. PGIC will be presented in a form of the visual analogue scale (VAS):

- -3 (Much Worse)
- -2
- -1
- 0 (No Change)
- 1
- 2
- 3 (Much Better)

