7.4.3 Visit 3 (End of Investigation)

This is Visit 5 for subjects who have participated in the Tolerance Phase. This visit should be conducted within ± 3 days after the completion of the 4-week IP use period.

Subjects and male partners will return to the clinical site after the 4-week IP use period, where the following assessments will be performed:

- Completion of FSFI by the subject
- Completion of an SPQ – Treatment Phase by the subject and the male partner
- Completion of Global Evaluation of Product Effectiveness, Tolerability and Usability by the subject
- Completion of PGIC by the subject and the male partner

- Physical examination, including gynaecological examination (if necessary, in the opinion of the Investigator)
- Collection of diary and review for compliance
- Collect and weigh returned IP
- [REDACTED]
- [REDACTED]
- Recording of AEs and concomitant medication changes (including the male partner)
- Recording subject's last menstrual period (the first date and the last date)

All assessments conducted during the Visit 3 are detailed in [Section 6](#) and summarised in Table 7-1. All clinical assessments and test results will be entered into each subject's eCRF.

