7.5 Unscheduled Visits

If unscheduled visits occur, the Investigator must record the reason for unscheduled visit, including any AEs/ADEs that the subject or the male partner has experienced since their last visit, concomitant medication changes, withdrawal (if deemed appropriate) and any clinical assessments deemed appropriate for their clinical care.

Unscheduled visits should not alter the timing of the routine investigation schedule.

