9.8 Handling of Missing Data and Drop-outs

All data will be analysed as collected; missing data due to premature discontinuation or any other reason will be left as missing. For the FSFI, in order to minimise the number of missing values for the FSFI subscale and Total scores, missing item responses will be handled as follows. A subscale score will be calculated as long as at least half of the items on the given subscale have valid, non-missing responses. Specifically, each subscale must have at least two non-missing responses, except for Desire, which has only two items and requires only one non-missing response. The Total FSFI score will be calculated as long as at least five out of the six subscale scores are present. Scores calculated in the presence of missing items will be pro-rated so that the theoretical minimum and maximum values are the same as those scores from complete data.

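### Women withdrawn during treatment, including for inadequate device performance, are asked for the Global Evaluation and PGIC but not for the FSFI, so they have no value in the primary paired test

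*Combined protocol and SAP*

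**What the plan says.** Section 4.5 lists reasons for removing a subject from the investigation. One is that, in the investigator's judgement, "it is in the subject's/male partner's best interest (this includes inadequate device performance". The only instruction there to obtain outcome data after an early exit is limited to one group: "For subjects who are lost to follow-up, at least 2 documented attempts should be made to contact the subjects for follow-up assessments". Those assessments are the Visit 3 set of the relevant phase, which for the Treatment Phase includes the FSFI.

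The treatment-phase instruments are handled differently at withdrawal:

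- Global Evaluation (6.12.4): "At the end of the Treatment Phase (or withdrawal if earlier) subjects will be asked to provide their global evaluation".
- PGIC (6.12.5): "At the end of the Treatment Phase (or withdrawal if earlier) subjects and male partners will be asked to complete a PGIC".
- FSFI (6.12.1): no withdrawal clause. The section notes that "The questionnaire requires a 4-week recall".

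The schedule in Table 7-1 places the FSFI at Treatment Phase Visits 2 and 3 only, and Section 7.4.3 lists "Completion of FSFI by the subject" at Visit 3. There is no early-termination visit. Section 7.5 foresees withdrawal at an unscheduled visit but asks only for "withdrawal (if deemed appropriate) and any clinical assessments deemed appropriate for their clinical care".

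On analysis, Section 9.5.1.1 uses a paired t-test within each arm, and Section 9.8 states that "missing data due to premature discontinuation or any other reason will be left as missing". Section 2.2 defines success as a change that is statistically significant and also clinically important, with +4 points as the threshold.

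**The concern.** Two secondary outcomes are collected at withdrawal and the primary one is not. A woman whom the investigator withdraws is in contact with the site and easier to ask than one who is lost, yet only the lost woman is to be pursued for the FSFI. Without a second FSFI she stays in the FAS by definition but contributes nothing to the paired test.

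One named reason for withdrawal is close to the outcome being measured, and the trial is open label. If some withdrawals happen because the product did little for the woman, the remaining change scores are a favourable selection. Each arm is judged against its own baseline, so no control arm offsets this. What is at stake is the comparison of the mean change with +4. No later imputation rule recovers a questionnaire that was never given.

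**Working it through.** **Inputs from the documents.** 33 randomised per arm, 10% attrition, 24 completers for 90% power (Section 3.3); 30 completers required (Section 4.5); +4 threshold (Section 2.2); two-sided test with Bonferroni-Holm over two arms, so 0.025 at the first step (Section 9.5.1.1).

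**The plan's own figure.** 30 × 1.10 = 33, and 33 × 0.90 = 29.7, about 30. The 33 is reproduced (30 / 0.90 rounds up to 34). The planned attrition is about 3 women per arm.

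**SD of change (assumption).** The SD is redacted. Taking 4 points as the powering effect, itself an inference because text is blacked out there, the noncentral t with n = 24, two-sided alpha 0.025 and power 0.90 needs a standardised effect of 0.7616. The implied SD is 4 / 0.7616 = 5.25.

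**Shift in the observed mean.** If w of 33 women are lost, the true mean is m and the lost women average f, the observed mean rises by w × (m − f) / (33 − w). Take m = 3.0 as an illustration.

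With nobody lost, the standard error is 5.25 / √33 = 0.914, and the chance that the observed mean reaches 4 is 1 − Φ(1 / 0.914) = 14%.

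The chances below come from simulating 200,000 groups of 33 from a normal distribution with mean 3 and SD 5.25.

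| Women lost | Average change of those lost | Shift | Chance of observing at least 4 |
|---|---|---|---|
| 3 at random from all 33 | 3.0 | 0 | 15% |
| 1 at random from the worst 11 | −2.6 | 5.6 / 32 = 0.17 | 19% |
| 3 at random from the worst 11 | −2.6 | 3 × 5.6 / 30 = 0.56 | 32% |
| 3 nearest zero change | about 0 | 3 × 3 / 30 = 0.30 | 24% |
| 3 worst | −6.0 | 3 × 9.0 / 30 = 0.90 | 46% |

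The first row is a control: smaller n alone does almost nothing. The last row is an upper bound for three losses. For an SD of 4.0 to 6.5 that bound runs from 0.69 to 1.12. The worst 11 of 33 lie on average 5.58 / 5.25 = 1.063 SD below the mean, so the shift for three women from the worst third is 3 × 1.063 × SD / 30, or 0.43 to 0.69 over the same range.

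**The same point without a distribution.** Suppose 30 completers average exactly 4.0 and the 3 lost women had zero change. The mean over all 33 is 30 × 4 / 33 = 3.64, and completers would have to average 33 × 4 / 30 = 4.40 for the mean over all 33 to reach 4.

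**Significance.** With those three zeros included and SD 5.25 among completers, the paired test over all 33 gives p of about 0.0003. The test against no change is not in danger; the reading against +4 is.

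**The case against.** **Few women may be affected.** The investigator may withdraw, and need not. There is no scheduled visit between dispensing at Visit 2 and the FSFI at Visit 3, and use is mainly at home, so poor performance would come to light early only through spontaneous contact or an unscheduled visit. Attrition also includes partner withdrawal, adverse events, deviations and pregnancy. This stands: giving all three planned losses to device failure is a pessimistic case, and a reader who infers that the plan systematically removes treatment failures goes further than the text.

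**The largest figure is extreme.** Losing the three worst women implies an average fall of about 6 FSFI points, which is marked deterioration and more than a product that failed to help. This also stands; 0.9 points and 46% are a bound, not an expectation.

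**The responder rate need not be inflated.** A reader might infer that it is. The plan does not state the denominator. If 15 women respond, 15/30 is 50% and 15/33 is 45%; with all FAS women in the denominator, a missing woman counts as a non-responder.

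**Mixed time points are inferred.** Section 9.5.2.1 summarises PGIC at the end of 4 weeks, and nothing says that values from early withdrawal are pooled into that table. The text merely leaves it open.

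**There is a reason not to take the FSFI early.** With a 4-week recall, a withdrawal-date score partly covers the run-in. That argues for the scheduled date, not for omitting the questionnaire. A week-4 score after withdrawal may reflect another lubricant, since the Table 4-1 restriction runs only to the end of the investigation; that limitation is real and has to be recorded.

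**Whether inadequate performance should be a ground for withdrawal is a clinical matter.** Agreed, and it is not questioned here.

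**Conclusion.** The gap in data collection is real and follows from the wording: no provision obtains the FSFI from a woman who is withdrawn rather than lost. Her missing value can be related to outcome, and the direction of concern is a mean change that looks too favourable against +4.

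The size is conditional. It assumes an SD of 5.25, back-solved with 4 points as the powering effect, a true mean of 3.0, and 1 to 3 losses per arm from the worst third. On those terms the shift is about 0.2 to 0.6 points, and the chance of observing at least 4 goes from 14% to about 19% to 32%. It also reads Section 2.2 as a comparison of the observed mean change with +4. The documents do not support a claim that many women will be withdrawn for this reason, that the responder rate is biased, or that the significance test is compromised. Confidence is high on the wording gap and modest on the size. The change should be made because it is cheap and protects the primary endpoint.

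**What to change.** Leave the withdrawal rule as it is and change only what is recorded and analysed.

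1. In Sections 4.5, 6.12.1 and 7.4.3, state that any woman withdrawn after IP dispensing who has not withdrawn consent is asked to complete the FSFI at her scheduled week-4 date. Record any other lubricant used since withdrawal.
2. Include that score in the FAS analysis.
3. Add a sensitivity analysis in which women with no week-4 FSFI are given zero change and counted as non-responders over all FAS subjects.
4. If only a withdrawal-date FSFI can be obtained, record its date and use it only in a sensitivity analysis, because its recall overlaps the run-in.
5. Report PGIC and Global Evaluation values taken at early withdrawal separately from the 4-week values.

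Cost: wording in three sections and in the analysis text, and one paper questionnaire for about 3 women per arm at the planned attrition. The downsides are that a post-withdrawal score may partly reflect other products, and that the observed mean change may be slightly less favourable.
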